3.1 Study design

[figure not shown]
This is an open, prospective, multicenter, randomized Phase III study.

78 patients will be randomized in several centers.

Experimental arm: REGIRI (arm A)

Control arm: Stivarga® (Regorafenib) (arm B)

First inclusion : september 2019Inclusion period : 64 months

End of the inclusion period: January 2025

Expected end of study: June 2025

Report : December 2025

3.2 Study period

3.3 Compensation modalities

The sponsor maintains clinical trial insurance coverage for this study in accordance with the laws and regulations of the country in which the study is performed.

4. Population

4.1 Number of planned patients

- -78 patients randomized out of approximately 312 screened patients.
- -Patients with wild-type or mutated RAS status and Genotype A/A of cyclin D1 (25% of patients).

4.2 Inclusion criteria

- 1. Signed informed consent obtained before any study specific procedures
- 2. Male or female ≥ 18 years of age
- 3. Histological documentation of adenocarcinoma of the colon or rectum
- 4. Patients with metastatic colorectal cancer
- 5. Progression during or within 3 months following the last administration of approved standard therapies, which must include a fluoropyrimidine (or raltitrexed), oxaliplatin, irinotecan, anti-VEGF therapy and an anti-EGFR therapy (for RAS wild-type tumors), encorafenib
- 6. ECOG performance status ≤1
- 7. Life expectancy of at least 3 months
- 8. Patients with A/A CCND1 genotype of rs603965 CCND1
- 9. Adequate bone marrow, liver and renal function as assessed by the following laboratory requirements conducted within 7 days of starting study treatment:

- Lipasémie ≤1.5 x ULN
- Total bilirubin ≤ 1.5 x ULN
- Alanine aminotransferase (ALT) and aspartate aminotransferase (AST) ≤ 3.0 x
 ULN (≤ 5 x ULN for patients with liver involvement of their cancer)
- Alkaline phosphatase (ALP) ≤ 2.5 x ULN (≤ 5.0 x ULN for patients with liver involvement for their cancer and/or have bone metastases)
- Platelet count ≥ 100,000/mm3; Hemoglobin (Hb) ≥ 9 g/dL; Absolute neutrophil count (ANC) ≥ 1,500/ mm3. Transfusion to meet the inclusion criterion will not be allowed
- Serum creatinine ≤ 1.5 x ULN
- 10. International normalized ratio (INR) \leq 1.5 x ULN and partial thromboplastin time (PTT) or activated partial thromboplastin time (aPTT) \leq 1.5 x ULN unless receiving treatment with therapeutic anticoagulation. Patients being treated with anticoagulant, e.g., heparin, will be allowed to participate provided no prior evidence of an underlying abnormality in these parameters exists. Close monitoring of at least weekly evaluations will be performed until INR and PTT are stable based on a predose measurement as defined by the local standard of care
- 11. Women of childbearing potential must have a blood or urine pregnancy test performed a maximum of 7 days before start of study treatment, and a negative result must be documented before start of study treatment
- 12. Women of childbearing potential and men must agree to use adequate contraception before entering the study until at least respectively 7 months and 4 months after the last study drug administration of Regorafenib and respectively 6 months and 3 months after the last study drug administration of Irinotecan. The investigator or a designated associate is requested to advise the patient on how to achieve an adequate birth control. Adequate contraception is defined in the study as any medically recommended method (or combination of methods) as per standard of care.

4.3 Non-inclusion criteria

- 1. Patients with A/G or G/G CCND1 genotype of rs603965 CCND1
- 2. Prior treatment with regorafenib or sorafenib
- 3. Prior treatment with TAS 102
- 4. Major surgical procedure, open biopsy, or significant traumatic injury within 28 days before start of study drug
- 5. Pregnant or breast-feeding subjects. Women of childbearing potential must have a pregnancy test performed a maximum of 7 days before start of treatment, and a negative result must be documented before start of study drug
- 6. Congestive heart failure ≥ New York Heart Association (NYHA) class 2 (appendix 3)
- 7. Unstable angina (angina symptoms at rest), new-onset angina (begun within the last 3 months)
- 8. Myocardial infarction less than 6 months before start of study drug
- 9. Cardiac arrhythmias requiring anti-arrhythmic therapy (beta blockers or digoxin are permitted)
- 10. Uncontrolled hypertension. (Systolic blood pressure > 140 mmHg or diastolic pressure> 90 mmHg despite optimal medical management)
- Pleural effusion or ascites that causes respiratory compromise (≥ CTCAE Grade 2 dyspnea)
- 12. Ongoing infection > Grade 2 CTCAE V5.0
- 13. Known history of human immunodeficiency virus (HIV) infection
- 14. Active hepatitis B or C, or chronic hepatitis B or C requiring treatment with antiviral therapy
- 15. Patients with seizure disorder requiring medication
- 16. History of organ allograft
- 17. Patients with evidence or history of any bleeding diathesis, irrespective of severity
- 18. Any hemorrhage or bleeding event ≥ CTCAE Grade 3 within 4 weeks prior to the start of study medication
- 19. Non-healing wound, ulcer, or bone fracture

- 20. Dehydration CTCAE V5.0 Grade ≥ 1
- 21. Substance abuse, medical, psychological or social conditions that may interfere with the subject's participation in the study or evaluation of the study results
- 22. Known hypersensitivity to any of the study drugs, study drug classes, or excipients in the formulation
- 23. Any illness or medical conditions that are unstable or could jeopardize the safety of the subject and his/her compliance in the study
- 24. Persistent proteinuria of CTCAE Grade 3 (> 3.5g/24 hours)
- 25. Patients unable to swallow oral medications
- 26. Any malabsorption condition
- 27. Chronic inflammatory bowel disease and / or bowel obstruction
- 28. Unresolved toxicity higher than CTCAE (V5.0) Grade 1 attributed to any prior therapy/procedure excluding alopecia, hypothyroidism and oxaliplatin induced neurotoxicity ≤ Grade 2
- 29. Concomitant participation or participation within the last 30 days in another clinical trial
- 30. Systemic anticancer therapy during this trial or within 4 weeks before randomization
- 31. Concomitant intake of St. John's wort
- 32. Live attenuated vaccines are prohibited 10 days before the treatment, during the treatment and 6 months after the termination of treatment
- 33. History of gastrointestinal fistula or perforation
- 34. Previous or concurrent cancer that is distinct in primary site or histology from colorectal cancer within 5 years prior to study inclusion, except for curatively treated cervical cancer in situ, non-melanoma skin cancer and bladder tumors [Ta (non invasive tumor), Tis (carcinoma superficial in situ and T1 (lamina propria invasion)

4.4 Procedure

Enrollment procedures will be performed using Electronic Case report Form (eCRF).

The procedure of use of eCRF for randomization will be given to all investigators during the study opening of each of the centers.

This enrolment procedure will be performed in 2 steps:

1/ Inclusion (screening): After inclusion and non-inclusion criteria have been fulfilled and the patient consent has been obtained, the patient will be included in the trial.

2/ Randomization: The randomization procedure will allocate the treatments A or B using list algorithm, with a 1:1 ratio and will be stratified by the following criteria:

-RAS Status

The inclusion / randomization will be performed using the module of the eCRF / Ennov Clinical® software. After the consent form has been signed and all inclusion/ non-inclusion criteria checked, the investigator will proceed with the randomization through the ICM online e-CRF:

https://ecrfcval.icm.unicancer.fr/CSOnline/

An automatic reply will be sent by e-mail to confirm the success of the randomization procedure to the:

- Representative of Sponsor project manager,
- Investigator,
- Data manager,
- Statistician,
- Pharmacist

Once the patient is registered, he/she is considered to be enrolled in the study.

5. Visit Schedule

5.1 Tabulated overview

Tabulated overview NEXT-REGIRI	Screening					Regorafenib (1 cycle = 4 weeks (1 cycle = every 15 days and 1 cycle = every 4 weeks)						Evaluation (Every 8 weeks)	End of treatment	Safety Follow-up ^c .	Follow-up	End of study
Baseline Documentation	As early as second- line	~ 28 days	Within 28 days	Within 14 days	Within 7 days	CX D1ª	C1, C2 D8	CX D1 ^a	C1, C2 D8	Cx D15	C1, C2 D22	~8 weeks	~14 days	~30 days	Follow-up: every other month	
Molecular testing informed consent	Х															
Clinical trial informed consent			Х													
Complete medical history			Х													
Inclusion/Exclusion Criteria			Х													
Physical examination					Χ	Χ		Χ		Χ			Χ			
β-HCG blood test					Χ	Χ		Χ								
Status of Ras, Raf and MSI have to be known		Χ														
Laboratory Studies																
12-lead ECG					Χ	X ¹		X ¹				Х	X ⁴			
Complete blood count					Χ	Χ		Χ		Χ			X ⁴			
Coagulation					Х	Х		Х		Х			X ⁴			
Electrolyte panel					Х	Х		Х		Х			X ⁴			
Chemistry panel					Χ	Х		Х		Х			X ⁴			

							,	Treatment							
Tabulated overview NEXT-REGIRI		Screening				Regorafenib (1 cycle = 4 weeks		e = every 15 d	EGIRI lays and 1 cy eeks)	cle = every 4	Every 8 weeks	End of treatment b,e	SafetyFollo w-up ^{c-d}	Follow- up	End of study
Liver function test panel				Х	X ²		Х	Χ	Χ	Х		X ⁴			
Thyroid function				Χ	Χ		Χ					X ⁴			
Tumor markers				Χ	X ³		X ³				Χ	X ⁴	X ⁵		
Urinary analysis				Χ	Χ		Χ		Χ			X ⁴			
Imaging assessments															
Radiologic Tumor assessment d		Х									Χ	X ⁶	X ⁵		
Other Clinical Assessments															
ECOG				Х	Х		Х		Χ			X ⁴			
Body weight, BSA, height, and vital signs				Х	Х		Х	X ⁷	Χ			X ⁴			
Concomitant medications			Х		Х		Χ		Χ			Χ	Х		
Adverse events				Χ	Χ		Χ	Χ	Х	Χ		Χ	Χ		
Drug dispensing					X8		X8								
Drug accountability					X8		X8		Χ			Х			
Post-study survival status														Х	
Anti-cancer medications														Х	
Patient's diary					X ⁹		X ⁹		Χ						
Patient Reported Outcomes															
Quality of life questionnaires					X ¹⁰		X ¹⁰				Χ				
Phone call : adverse events, blood pressure					Х	Х				X					
Ancillary study															
Immunohistochemistry ^e															X

- a: Cycle 1 Day 1 : the laboratory evaluations are not required at day 1 of cycle 1 if those were completed within 7 days
- b: Within 14 days (+/- 7 day) after study treatment has stopped
- c: Within 30 days (+/- 7 day) after study treatment has stopped
- d: CT scan of the abdomen, pelvis and chest or hepatic MRI and CT scan of the pelvis and chest without injection; RECIST criteria version 1.1
- e: Paraffin-embedded human solid tissue blocks will be sent off at room temperature at the end of the inclusions
- 1: A 12-lead ECG will be performed at the end of every other cycle (8 weeks, if there's no postponed treatment)
- 2: D1 and D15 of the first two cycles for Bras B (Stivarga®) and D1 only at the other cycles
- 3: Tumor markers CEA and CA 19-9 at every cycle
- 4: If the last clinical and laboratory evaluations > 7 days
- 5: if not done at the EOT visit
- 6: If the last radiological tumor assessment > 1 month
- 7: C1-C2 D8 (arm A): vital signs without height, weight and BSA
- 8: As applicable
- 9: A treatment diary will be handed over to patient on cycle 1 day 1
- 10: EORTC QLQ-C30 questionnaires will be completed by the patient on Day 1 of Cycle 1 then at each evaluation (= 8 weeks) for both treatments

5.2 Screening period

Enrollment into NEXT-REGIRI will be performed in two stages with two separate informed consent forms. Initially, all potential patients will consent to undergo molecular testing (appendix 4). The blood sample for molecular testing will be sent off to:

[name] [name] Blood collection manager

Institut régional du cancer de Montpellier Centre de ressources biologiques [name]

[contact] – [contact] [contact]

The molecular testing will be carried out by [name].

[name]
Responsable de l'unité de recherche translationnelle
Institut régional du cancer de Montpellier

Protocole NEXT-REGIRI -Version 6.0 du 09/11/2023

Page **27** sur **86**

Unité de recherche translationnelle [name]

[contact] – [contact] [contact]

Only patients with the Sequence A/A rs603965 of cycline D1 gene can be screened for the study treatment (REGIRI vs Regorafenib). A second consent form to screen for the clinical study (Clinical Trial Consent).

Both consent processes are independent of each other.

The following procedure will be able to be performed as early as second-line treatment:

 A blood sample will be collected into a PAXGENE DNA tube then will be shipped to CRB-ICM for determining the variant A/A genotype of cyclin D1

The following procedures and assessments will be performed around 28 days of starting study Drug for both arms of treatment:

- Status of RAS, RAF and MSI have to be known
- Obtainment of molecular testing informed consent

The following procedures and assessments will be performed within 28 days of starting study Drug for both arms of treatment:

- Obtainment of written informed consent. No screening procedures may be performed unless written informed consent has been obtained
- Inclusion/Exclusion criteria checked
- Radiological tumor assessment using the RECIST criteria, version 1.1 (see Appendix 5) must be performed. (CT scan of the abdomen, pelvis and chest or hepatic MRI and CT scan of the pelvis and chest without injection).
 - A PET scan is not acceptable for radiological evaluation

 All additional suspected sites of disease should be imaged. An appropriate radiological evaluation should be obtained if bone metastases are suspected (e.g., bone scan)

 Complete medical history including demographics, allergies, prior surgery and prior chemo/radiation therapy with documentation of treatment response.

The following procedures and assessments will be performed within 14 days of starting study drug:

 Record of all concomitant medications except Homeopathy. All medicines and significant non-drug therapies taken within 14 days before study treatment must be recorded in the e-CRF.

The following procedures and assessments will be performed within 7 days of starting study drug:

12-lead ECG

• ECOG performance status (Appendix 6)

Adverse events

Physical examination including review of all organ systems, examination of pertinent organ systems, vital signs (heart rate, blood pressure, weight, BSA and height).
 The blood pressure measurements must be performed in a consistent manner using a manual cuff on the same arm. The assessment must be made with the patients in the sitting position using the same arm for all evaluations. Two additional measurements, taken 5 minutes apart, should be conducted if the first blood pressure

is abnormal

 A CBC with differential should be performed: RBC, hemoglobin, hematocrit, platelet count and WBC. WBC must include differential neutrophil, lymphocyte, monocyte, basophil and eosinophil counts

- Electrolyte panel: sodium, potassium, calcium, chloride
- Chemistry panel: albumin, lipase, phosphate, glucose, serum creatinine, clearance calculated according CKD-EPI (appendix 7)
- Liver function test panel: Aspartate Amino-Transferase (AST), Alanine Amino-Transferase (ALT), bilirubin (total and direct), alkaline phosphatase, GGT, Lactic Dehydrogenase (LDH)
- Thyroid function test: TSH, free T3, and free T4
- Coagulation panel: Prothrombin time (PT) or the International Ratio of PT (PT-INR) and Partial Thromboplastin Time (PTT)
- Urine analysis: Urine analysis by urinary dipstick. If results of protein ≥ 3+,
 quantification of proteinuria on a 24-hour urine collection
- Tumor markers: CEA (Carcino-Embryogenic Antigen), CA 19.9 (Carbohydrate Antigen 19-9)
- A β-HCG dosage for women of childbearing potential. Post-menopausal women with no menses for at least 1 year or surgically sterilized women will not be required to undergo a pregnancy test.

5.3 Treatment period

REGIRI or Regorafenib:

After all screening assessments have been completed and the patient's eligibility has been confirmed and documented, the patient will be randomized.

The following assessments should be performed on the first day and day 15 of each cycle (REGIRI) or cycle (Regorafenib) except C1D1 prior to receiving study treatment (+/- 3 days):

- Physical examination with weight, body surface area (if the patient's body weight changes by more than 10 % then BSA will be recalculated for Regorafenib and it will be recalculated for any change of weight for Irinotecan) and vital signs (heart rate, blood pressure)
- ECOG performance status :
- Adverse events documentation (including Start/Stop dates, seriousness, CTC notation and grading, relationship to study drug, outcome and action taken) using CTCAE V5.0
- Concomitant medications (including start/stop dates, dose, indication)
- 12-lead ECG. It will be performed every other cycle (8 weeks if there's no postponed treatment) for both arms
- The following laboratory evaluations are not required at Day 1 of Cycle 1 if these
 were completed within 7 days of starting study drug treatment. Otherwise, these
 laboratory evaluations are required on Day 1 and 15 of each cycle:
 - → CBC with differential should be performed: RBC, hemoglobin, hematocrit, platelet count and WBC. WBC must include differential neutrophil, lymphocyte, monocyte, basophil and eosinophil counts
 - → Coagulation panel: Prothrombin time (PT) or the International Ratio of PT (PT-INR) and Partial Thromboplastin Time (PTT)
 - → Electrolyte panel: sodium, potassium, chloride, calcium
 - → Chemistry panel : albumin, lipase, phosphate, glucose, serum creatinine, clearance calculated according CKD-EPI (appendix 7)
 - → Hepatic panel: Aspartate Amino-Transferase (AST), Alanine Amino-Transferase (ALT), bilirubin (total and direct), GGT, alkaline phosphatase, Lactic Dehydrogenase (LDH)

- → Thyroid function test (TSH, free T3, free T4, on day 1 of each cycle for both arms)
- Tumor markers CEA (Carcino-Embryogenic Antigen), CA 19-9 (carbohydrate Antigen 19-9) every cycle for both treatments
- A β-HCG dosage for women of childbearing potential. Post-menopausal women with no menses for at least 1 year or surgically sterilized women will not be required to undergo a pregnancy test (on day 1 of each cycle for both arms).
- Urine analysis by urinary dipstick. If results of protein ≥ 3+, then quantification
 of proteinuria on a 24-hour urine collection must be done.
- EORTC QLQ-C30 (appendix 2) questionnaires will be completed by the patient on Day 1 of Cycle 1 (baseline) then on the first day of every other cycle (every 8 weeks)
- Drug dispensing
- Drug accountability (pharmacy). To have complete control over the distribution and use of the study drug, the drug accountability must be performed on Day 1 for arm A (REGIRI) and B (Regorafenib) of each cycle

Provide patient's diary on C1D1. It will allow to patient to write down his oral intakes and blood pressure values

The blood pressure must be monitored weekly for the first six weeks of study treatment. The blood pressure will be recorded by the patient and entered onto his treatment diary. In the latter case, the patient should be instructed to contact the physician in the event of systolic \geq 150 mm Hg and / or diastolic \geq 100 mm Hg. The physician should confirm the reading before recording it into the e-CRF. Blood pressure measurements will be performed in patients sitting for 5 minutes prior to the evaluation. The patient should be instructed to take their blood pressure in the morning and repeat two more times for accuracy.

The following assessments should be performed on day 8 of cycle 1 and 2:

REGIRI (arm A)

- Vital signs (Heart rate and blood pressure)
- these laboratory evaluations are required: Aspartate Amino-Transferase (AST), Alanine Amino-Transferase (ALT), bilirubin (total and direct)

Stivarga® (Regorafenib) (arm B):

• Phone call by a treatment nurse for knowing if there are any adverse events and blood pressure value (current state of the art)

The following assessments should be performed on day 15 of cycle 1 and 2:

REGIRI (arm A)

- Physical examination with weight and vital signs (heart rate, blood pressure)
- ECOG performance status
- Concomitant medications (including start/stop dates, dose, indication)
- Adverse events documentation (including Start/Stop dates, seriousness, CTC notation and grading, relationship to study drug, outcome and action taken) using CTCAE V5.0
- A CBC with differential should be performed: RBC, hemoglobin, hematocrit, platelet count and WBC. WBC must include differential neutrophil, lymphocyte, monocyte, basophil and eosinophil counts
- Coagulation panel: Prothrombin time (PT) or the International Ratio of PT (PT-INR) and Partial Thromboplastin Time (PTT)
- Electrolyte panel: sodium, potassium, chloride, calcium

- Chemistry panel: albumin, lipase, phosphate, glucose, serum creatinine, clearance calculated according CKD-EPI (appendix 7)
- Hepatic panel: Aspartate Amino-Transferase (AST), Alanine Amino-Transferase (ALT), bilirubin (total and direct), GGT, alkaline phosphatase, Lactic Dehydrogenase (LDH)
- Urine analysis by urinary dipstick. If results of protein ≥ 3+, then quantification of proteinuria on a 24-hour urine collection must be done.
- Drug accountability (pharmacy)
 Verify patient's diary. It will allow to patient to write down his oral intakes and blood pressure values

The following assessments should be performed on day 15 of cycle 1 and 2:

Stivarga® (Regorafenib - arm B):

• these laboratory evaluations are required: Aspartate Amino-Transferase (AST), Alanine Amino-Transferase (ALT), bilirubin (total and direct)

The following assessments should be performed on day 22 of cycle 1 and 2:

REGIRI (arm A):

- Phone call by a treatment nurse for knowing if there are any adverse events and blood pressure value (current state of the art)
- These laboratory evaluations are required: Aspartate Amino-Transferase (AST),
 Alanine Amino-Transferase (ALT), bilirubin (total and direct)

The following assessments should be performed at each evaluation i.e (every 8 weeks):

REGIRI or Regorafenib:

 Tumor markers CEA (Carcino-Embryogenic Antigen), CA 19.9 (Carbohydrate Antigen 19-9)

 Radiological tumor assessment using the RECIST criteria, version 1.1 (see Appendix 5) must be performed. (CT scan of the abdomen, pelvis and chest or hepatic MRI and CT scan of the pelvis and chest without injection)

A PET scan is not acceptable for radiological evaluation. Throughout the study, the identical lesions to those identified and measured at baseline must be evaluated using the same technique, and preferably by the same radiologist. Copies of all CT scans performed for tumor assessment in non-progressive enrolled patients will be stored on CDs at the site

 EORTC QLQ-C30 (appendix 2) questionnaires will be completed by the patient at each evaluation i.e 8 weeks

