6.1 Experimental treatment or procedures

Experimental arm: REGIRI (arm A)

[figure not shown]

Figure 1: REGIRI regimen

The treatment schedule will be as follows:

- Starting on days 1 and 15 of each 28-day cycle, all patients will receive irinotecan as an intravenous infusion over a 90 minute period.

The initial dose of irinotecan will be 120 mg/m².

The dose for the second infusion of irinotecan will be 150 mg/m² over 90 minutes if no diarrhea of grade >1 NCI-CTCAE V 5.0 grading or others toxicities of grade >2 occur.

The dose for the third and subsequent infusions of irinotecan will be 180 mg/m² over 90 minutes under the same conditions as for the 2nd infusion.

- -On days 2–8 and 16–22 of each cycle, all patients will receive Regorafenib 160 mg orally once daily.
- -A chemotherapy course = 15 days, 1 cycle = 4 weeks

Control arm: Stivarga® (Regorafenib) (arm B)

-Regorafenib will be given orally at a dose of 160 mg once daily over 3 weeks then one week off.

1 cycle = 4 weeks

[figure not shown]

Figure 2: Regorafenib schedule

The following products will be used in the study:

- Regorafenib, 40 mg tablets
- Irinotecan, 180 mg/m² IV (20 mg/ml)

ARM A: REGIRI (Regorafenib + Irinotecan)

Irinotecan

See manufacturer's product information (Appendix 8).

Irinotecan will be prescribed by each center and used in its marketed form.

The irinotecan will be diluted in a 5 % glucose solution or a 0.9% sodium chloride solution. The irinotecan will be delivered over 90 minutes as an intravenous infusion.

Regorafenib

For Packaging, List of excipients and Storage: See Investigator's brochure (Appendix 8).

Regorafenib® will be provided by Sponsor as tablets of 40 mg.

The investigational product(s) label will bear sponsor's name, address and telephone number, the EudraCT number, product name, dosage form and strength, quantity of investigational product par container, batch number, expiration date, dosing instructions, required storage conditions and required caution statements and/or regulatory statements as applicable.

Protocole NEXT-REGIRI -Version 6.0 du 09/11/2023

Page 39 sur 86

Receipt, distribution, return and destruction (if any) of the study drug must be properly documented.

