PRO data as measured by the EORTC QLQ-C30 (appendix 2) will be analyzed to assess differences in health-related quality of life (HRQOL) values between treatment arms.

HRQOL scores were described for each assessment and compared either between treatment arms (rank sum test). The missing data pattern was studied by the comparison of the baseline characteristics between patients who either completed baseline HRQOL questionnaires or not. The compliance of the patients was also described using fill rate at each visit and for each questionnaire.

Longitudinal analyses were performed using two approaches:

- (1) A LMM analysed the evolution of scores through time and combined fixed effects [Cnaan A, Laird NM, Slasor P. Using the general linear mixed model to analyse unbalanced repeated measures and longitudinal data. Stat Med 1997;16:2349-80.+ Fairclough DL. Design and analysis of quality of life studies in clinical trials. 2002.] for study group, time factors, treatment-by-time interaction effects and random effects allowing specific correlations between observations for a particular patient. This mode I assumed no difference between the treatment arms at baseline.
- (2) A time to event approach considered the definitive deterioration of a HRQOL score as an event. Osoba et al. [Osoba D, Rodrigues G, Myles J, Zee B, Pater J.

Interpreting the significance of changes in health-related quality-of-life scores. J Clin Oncol 1998;16:139-44.] showed that a mean change of 5-10 pts, 10-20 pts and >20 pts in a QLQC30 score corresponds to a "small", "moderate" and "large" change in HRQOL. This definition was applied to indicate the clinical relevance of any differences. TUDD was defined as the time from randomisation to the first score deterioration with a 10-point minimal

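### The only baseline QLQ-C30 is taken after open-label randomisation, yet the mixed model assumes equal baselines and TUDD is measured from that score

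*Combined protocol and SAP*

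**What the plan says.** **Design and order of events.** Section 3.1: "This is an open, prospective, multicenter, randomized Phase III study". Section 5.3 opens the treatment period with randomisation: "After all screening assessments have been completed and the patient's eligibility has been confirmed and documented, the patient will be randomized". Section 4.4 adds: "An automatic reply will be sent by e-mail to confirm the success of the randomization procedure to the" sponsor's project manager, the investigator, the data manager, the statistician and the pharmacist.

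**Questionnaire timing.** Section 5.3: "EORTC QLQ-C30 (appendix 2) questionnaires will be completed by the patient on Day 1 of Cycle 1 (baseline", then every 8 weeks. Footnote 10 to the schedule in section 5.1 agrees: "EORTC QLQ-C30 questionnaires will be completed by the patient on Day 1 of Cycle 1 then at each evaluation". The screening lists in section 5.2 contain no questionnaire.

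**Day 1 differs visibly between arms.** For arm A, section 6.1 says: "Starting on days 1 and 15 of each 28-day cycle, all patients will receive irinotecan as an intravenous infusion over a 90 minute period". Arm B takes tablets only.

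**Use of the score.** In section 9.3 the longitudinal mixed model "assumed no difference between the treatment arms at baseline". The second approach is a time-to-event analysis: "TUDD was defined as the time from randomisation to the first score deterioration with a 10-point minimal" clinically important difference, judged against the baseline score.

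**The concern.** A model that sets the arms equal at baseline is justified by randomisation, but only for measurements made before it. Here the measurement comes after it, in a trial where the patient can be expected to know whether the allocation is the combination or regorafenib alone. If patients in one arm answer differently because of that knowledge (disappointment in one arm, apprehension or hope in the other), the difference enters the baseline score.

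That score is used in both planned longitudinal analyses. In the mixed model it is constrained to be equal between arms. In TUDD it sets each patient's 10-point threshold. TUDD has a further mismatch: its clock starts at randomisation, while its reference score is taken later.

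What is at stake is the between-arm quality-of-life comparison, a secondary endpoint.

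**Working it through.** The protocol gives no figure to reproduce, so the check is first textual and then illustrative.

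**1. Order of events.** Screening without a questionnaire (5.2) → randomisation (4.4, 5.3) → Cycle 1 Day 1 with the baseline QLQ-C30 (5.1 footnote 10, 5.3). Nothing asks for the form before the patient learns the arm. Whether it must precede the first dose is also unclear, because the lead-in to the Day 1 and Day 15 list in 5.3 mentions assessment before treatment but makes an exception for C1D1.

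**2. Mixed model.** Take two time points, equal variances and within-patient correlation rho. Forcing equal baselines is then equivalent to

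estimate = (follow-up difference between arms) − rho × (baseline difference between arms).

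Suppose the true effect is zero, and allocation shifts one arm's baseline by d points and has faded by the next form at 8 weeks. The bias is then rho × d in absolute size. Both d and rho are assumptions; neither is in the documents.

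| d | rho | rho × d | simulated |
|---|---|---|---|
| 3 | 0.5 | 1.5 | 1.51 |
| 3 | 0.7 | 2.1 | 2.12 |
| 5 | 0.5 | 2.5 | 2.46 |
| 5 | 0.7 | 3.5 | 3.51 |

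**3. Deterioration threshold.** Further assumptions are SD 20, a mean decline of 3 points in both arms, and higher scores being better. This looks at one follow-up form, not the full definitive-deterioration rule. The change score has SD 20 × √(2(1 − rho)), which is 20 at rho = 0.5.

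- Unshifted arm: P(drop ≥ 10) = Φ((−10 + 3)/20) = Φ(−0.35) = 0.36.
- Arm with baseline lowered by d = 5: P = Φ((−10 + 3 − 5)/20) = Φ(−0.60) = 0.27. Simulation gives 0.275 against 0.362.
- With d = 3: Φ(−0.50) = 0.31. Simulation gives 0.309 against 0.364.
- With d = 0, as a form completed before randomisation would guarantee: 0.363 against 0.364.

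**4. What if the reaction lasts?** If the shift d is still fully present at follow-up, the same algebra gives a different pattern (absolute size, true effect zero, complete data):

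| Analysis | Reaction fades | Reaction persists |
|---|---|---|
| Constrained model, C1D1 baseline | rho × d | (1 − rho) × d |
| Change from baseline or treatment-by-time interaction, C1D1 baseline | d | 0 |
| Follow-up levels, no constraint, C1D1 baseline | 0 | d |
| Constrained model, pre-randomisation baseline | 0 | d |

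Row 2 determines which sensitivity analysis is useful. Dropping the constraint and then reading the interaction carries the whole of d when the reaction fades, which is more than the rho × d it was meant to remove.

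**The case against.** **Knowledge of the arm is inferred.** No section says when the patient is told, and the e-mail in 4.4 goes to staff. This is correct. The open design, the notice to the investigator and the Day 1 infusion in one arm only make knowledge by C1D1 very probable, but no more than that.

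**No shift is shown.** The documents support neither a size nor a direction, and the mixed-model figures of 1.5–3.5 points lie below the 5–10 points that section 9.3 calls a small change. This also stands. The numbers are illustrations, and the TUDD threshold is the more sensitive of the two.

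**The bias depends on the reaction fading.** If it persists, a C1D1 baseline cancels it in change scores and TUDD, while a pre-randomisation baseline lets it show as a treatment difference. This stands as a limit. Moving the form makes the equal-baseline assumption valid; it does not cure open-label reporting at follow-up.

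**The constraint itself is unclear.** Section 9.3 lists a study-group effect alongside time and their interaction, which would ordinarily allow a baseline difference, and also says none is assumed. So rho × d applies only if the model is in fact constrained. The SAP, due before database lock, can settle this.

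**Patients who never start treatment.** A reader might infer that the C1D1 timing costs the analysis these patients. The documents give little support: later forms are tied to the 8-week evaluations, and none is listed at end of treatment or follow-up. Such patients would probably have no later score either. Section 9.3 also already plans to compare patients with and without a baseline form.

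**Conclusion.** The concern holds as a risk built into the design. The sole baseline QLQ-C30 follows randomisation in an open trial, and both longitudinal quality-of-life analyses use it in ways that randomisation does not protect. The size and direction of any bias are unknown. Under assumed d = 3–5 and rho = 0.5–0.7, with a reaction that fades by 8 weeks, a constrained model would be off by 1.5–3.5 points, and the TUDD threshold would move by 3–5 of its 10 points in one arm.

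A reader might infer that the baselines are known to be contaminated, or that the quality-of-life comparison is invalid. The documents do not support either: they do not state when patients learn the arm and do not show that any shift occurs. Quality of life is one of several secondary endpoints, and the overall survival comparison is untouched.

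**What to change.** **Remaining patients.** In sections 5.1, 5.2 and 5.3, move the baseline QLQ-C30 to the screening visit within 7 days of treatment start, after trial consent and before randomisation. It is the same form at an existing visit, and it makes equal baselines true by design.

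**Patients already enrolled on a C1D1 baseline.** Specify in the SAP:

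- a sensitivity mixed model without the equal-baseline constraint, reporting the between-arm difference in follow-up levels, not change from baseline or the treatment-by-time interaction;
- a TUDD sensitivity analysis by baseline timing (before or after randomisation), which requires the date of each baseline form to be recorded against the randomisation date;
- a plain statement of whether the main model is constrained, given the study-group effect it lists.

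**Cost.** A small amendment, and two baseline timings within the 78 patients. The reach is limited: version 6.0 is dated November 2023 and inclusion runs from September 2019 to January 2025, so about 50 of the 64 months had passed. For most patients the analysis safeguards are therefore what is available.
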